10.1.2.3. Thyroid Function

Blood for thyroid-stimulating hormone (TSH), Free T4 and T3 will be drawn in studies of Probody Tx that may induce an immune response.

10.1.2.4. Immune Safety Assays

In studies of Probody Tx that may induce an immune response, testing may include: free T4 and T3, rheumatoid factor (RF), adrenocorticotrophic hormone (ACTH), C-reactive protein (CRP), antinuclear antibody (ANA) titer and pattern.

The following tests, may also be performed on selected stored samples at a later date: anti-DNA antibody, anti-phospholipid antibody, anti-SSA antibody (Ro), anti-islet cell antibody; anti-SSB antibody (La), anti-neutrophil cytoplasm antibody, anti-thyroglobulin antibody, C3 and C4, anti-LKM antibody, and CH50.

Abnormal endocrine results should be followed up with prolactin and a.m. cortisol tests, and may require an endocrine consult and additional testing.

10.1.2.5. Coagulation

Coagulation samples will be evaluated for prothrombin time (PT), partial thromboplastin time (PTT), and international normalized ratio (INR).

10.1.2.6. Urinalysis

Urinalysis will include assessment of protein, blood, leukocytes, glucose, ketones, bilirubin, urobilinogen, pH, and specific gravity, plus microscopic exam.

10.1.2.7. Pregnancy

Pregnant women are not eligible for inclusion in the study. A serum pregnancy (human chorionic gonadotropin [HCG]) should be evaluated in all WOCBP. Urine pregnancy tests may be performed in lieu of serum pregnancy tests while the subject is on treatment.

10.1.3. Other Safety Measures

10.1.3.1. Vital Signs

Vital signs will include heart rate and blood pressure (supine), temperature, respiratory rate, and pulse oximetry.

Weight and height will be measured.

10.1.3.2. Electrocardiogram (ECG)

12-lead ECGs should be obtained, in triplicate (approximately 2-5 minutes apart), in digital format (when possible), and archived, while supine at screening, at time points to be specified in the Probody Tx-specific Module.

10.1.3.3. Physical Exam

A complete physical examination includes assessment of the skin, head, eyes, nose, throat, neck, joints, lungs, heart, abdomen (including liver and spleen), lymph nodes, and extremities. A brief neurological examination should also be performed. A limited, targeted physical exam should be performed as needed by subject symptoms or clinical observations, focused on key organ systems of interest (eg, cardiovascular [CV], pulmonary, gastrointestinal [GI], skin, ophthalmic, or any systems with previously noted abnormal findings).

10.1.3.4. Ophthalmology Exam

Where applicable, a complete ophthalmology exam will be performed by a board-certified ophthalmologist at baseline, post-treatment and as specified in the Probody Tx-specific module and will include visual acuity, indirect fundoscopy, slit lamp examination under dilatation, intraocular pressure measurement and corneal photography (not required at baseline). Baseline testing will also include Schirmer's test. Subjects will be asked about ocular symptoms such as a history of dry eye and contact lens use and an ocular symptom assessment (blurred vision, ocular discomfort, etc) will be performed.

10.1.3.5. Concomitant Medications/Therapies

Concomitant medications/therapies will be recorded.

10.1.3.6. Eastern Cooperative Oncology Group (ECOG) Performance Status

The ECOG performance status ([Appendix 16.1](#)) will be evaluated during the study.

10.2. Efficacy

Although response is not the primary endpoint of the Phase 1-2 trials conducted under the Common Core Document, tumor response will be assessed by standard criteria to obtain a preliminary estimate of anti-cancer efficacy for the Probody Tx (as monotherapy and/or as combination therapy) in subjects with advanced or unresectable solid tumors. Additional criteria specific to a cancer (eg, the Lugano Classification for lymphomas) will be outlined in the Probody Tx-specific Module, as applicable.

Efficacy parameters may include:

- ORR (RECIST version 1.1 and, as applicable, modified immune-related RECIST [irRECIST] criteria)
- TTR
- DOR
- PFS
- OS

Efficacy will be assessed by RECIST v1.1 (and modified irRECIST for agents thought be immune-active as guided by the drug-specific module), if applicable.

10.2.1. Imaging

Computerized (or computed) tomography (CT) with and/or without contrast or magnetic resonance imaging (MRI) will be performed as appropriate. Bone scans and positron emission tomography (PET) scans may be performed if clinically indicated, but may not be used to measure target lesions. Imaging methods will be employed consistently during the course of each subject's evaluation during the study.

10.2.2. Tumor Markers

Blood draws for tumor makers will be outlined in the module, as applicable.

10.2.3. Response Criteria

RECIST v1.1 guidelines ([Eisenhauer et al, 2009](#)) will be used to evaluate response to therapy. Other tumor-specific response criteria will be utilized, as applicable, as well as modified irRECIST criteria ([Bohnsack et al, 2014](#)) for agents thought to be immuno-active.

Imaging of the chest, abdomen, and pelvis (as applicable) is required within 30 days prior to the first administration of Probody Tx. CT and magnetic resonance imaging (MRI) are acceptable. Subjects with skin, subcutaneous or lymph node metastases may also have tumor evaluations (including measurements with a ruler) by means of physical examination. During Screening, subjects must have disease that is measurable by standard imaging techniques or evaluable, per RECIST v1.1. For subjects who have received prior radiation therapy, measurable lesions must be outside of any prior radiation field(s), unless disease progression has been documented at that disease site subsequent to radiation.

In subjects for whom a baseline scan indicates no evidence of pelvic malignancy, chest/abdomen imaging may be performed (without pelvic imaging) at subsequent evaluations. In selected situations, a combination of CT/MRI is acceptable (ie, CT of chest, MRI of abdomen). The same imaging modalities used to characterize each site of disease at baseline should be used throughout the duration of the study. Imaging of extremities is also permitted and is required if significant metastases are present and are optimally evaluated via CT/MRI of an extremity.

Unless otherwise specified in the Probody Tx-specific Protocol Module Schedule of Events, tumor measurements and disease response assessments are to be performed every 8 weeks after the first dose of study drug through 12 months of treatment and then every 12 weeks from Month 13 until development of progressive disease (PD). Additional assessments may be performed during follow-up and will be specified in the Probody Tx-specific Protocol Module. Tumor measurements and disease response assessment are to be performed at the EOT visit as well.

Anatomical measurements (summed across target lesions) will be documented. When possible, the same qualified physician should interpret results to reduce variability. Radiographic images will be maintained at the study center, and Investigator findings will be filed in the subject's source documents.

10.2.3.1. RECIST v1.1

Assessment of Measurable, Non-measurable, Target and Non-Target Lesions

During Screening, tumor lesions are to be categorized as measurable versus non-measurable and target versus non-target, as follows.

Measurable versus non-measurable

- Measurable lesions can be accurately measured in at least one dimension (longest diameter [LD] to be recorded) with a *minimum* size of: 10 mm by CT or MRI scan for non-nodal lesions and ≥ 15 mm in short axis for nodal lesions, 10 mm caliper measurement by clinical exam, or 20 mm by chest X-ray (CXR).
- Non-measurable: all other lesions, including small lesions (longest diameter < 10 mm or pathological lymph nodes with ≥ 10 to < 15 mm short axis) and truly non-measurable lesions (eg, pleural or pericardial effusion, lymphangitic involvement of skin or lung).

Target versus non-target

- Target: all measurable lesions up to a maximum of 2 lesions per organ and 5 lesions in total, representative of all involved organs, are to be identified as target lesions and measured and recorded at Screening. Target lesions are to be selected on the basis of their size (ie, those with the longest diameter) and suitability for accurate repeated measurement. The sum of the longest diameter for all target lesions is to be calculated and recorded in the eCRF as the baseline sum longest diameter. Target lesions cannot be biopsied at any time during the study.
- Non-target: all other lesions not classified as target lesions (or sites of disease) are to be identified as non-target lesions and are to be recorded in the eCRF. Measurement of non-target lesions is not required.

Disease response in target and non-target lesions will be assessed by the Investigator using RECIST v1.1 ([Eisenhauer et al, 2009](#)), according to the categories and criteria described in the table below. The best overall response for each subject will be reported as the best response documented over the sequence of objective statuses recorded using the categories and criteria in [Table 3](#).

10.2.4. Definitions of Treatment Outcomes: RECIST v1.1

Table 3: Response Evaluation Criteria in Solid Tumors (RECIST) Guidelines for Tumor Response

Disease Response Criteria for Target and Non-Target Lesions	
Evaluation of Target lesions	
Complete Response (CR):	Disappearance of all target lesions.
Partial Response (PR):	At least a 30% decrease in the sum of the LD of target lesions, taking as reference the baseline sum LD.
Stable Disease (SD):	Neither sufficient shrinkage to qualify for PR nor sufficient increase to qualify for PD, taking as reference the smallest sum LD since the treatment started.
Progressive Disease (PD):	At least a 20% increase in the sum of the LD of target lesions, taking as reference the smallest sum LD recorded since the treatment started or the appearance of one or more new lesions.
Evaluation of Non-target lesions	
Complete Response (CR):	Disappearance of all non-target lesions and normalization of tumor marker level.
Incomplete Response/ Stable Disease (SD):	Persistence of one or more non-target lesion(s) or/and maintenance of tumor marker level above the normal limits.
Progressive Disease (PD):	Appearance of one or more new lesions and/or unequivocal progression of existing non-target lesions.

Source: [Eisenhauer et al, 2009](#)
Key: LD = longest diameter

Table 4: Overall Response Criteria (RECIST v1.1)

Subjects with Target and Non-Target Lesions			
Target Lesions	Non-Target Lesions	New Lesions	Overall Response
CR	CR	No	CR
CR	Non-CR / Non-PD	No	PR
CR	Not evaluated	No	PR
PR	Non-PD or not all evaluated	No	PR
SD	Non-PD or not all evaluated	No	SD
Not evaluated	Non-PD	No	NE
PD	Any	Yes or no	PD
Any	PD	Yes or no	PD
Any	Any	Yes	PD
Subjects with Non-Target Lesions Only			
Non-Target Lesions		New Lesions	Overall Response
CR		No	CR
Non-CR / Non-PD		No	Non-CR / Non-PD
Not all evaluated		No	NE
Unequivocal PD		Yes or No	PD
Any		Yes	PD

Source: [Eisenhauer et al, 2009](#)

Key: CR = complete response; NE = not evaluable; PD = progressive disease

Any subject with a CR or PR is to have repeat assessments performed no earlier than 4 weeks later to confirm the response.

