10.2.4.1. Modified immune-related RECIST (irRECIST)

As noted by [Bohnsack et al \(2014\)](#), RECIST v1.1 has some limitations when applied to immunotherapy in oncology. Tumors that appear to have progressed by RECIST criteria may later regress, possibly reflective of the impact of immune agents on host antitumor response ([Chiou & Burotto, 2015](#)).

Modified irRECIST criteria ([Appendix 16.2](#)) will be used to evaluate tumor response. Definitions for measurable, non-measurable, target and non-target lesions are outlined in [Section 10.2.3.1](#).

The [Bohnsack et al \(2014\)](#) modifications of the iRECIST criteria differ from the immune-related Response Criteria (irRC) as noted by [Wolchock et al \(2009\)](#) as follows:

1. At the time of unconfirmed progression, the baseline is reset and the immune-related Progressive Disease (irPD) is only achieved if an increase in tumor burden of 20% relative to the new baseline is observed.
2. Target lesions cannot be biopsied at any time during the study.

Table 5: Derivation of modified irRECIST Overall Responses

TMTB of all measurable and new measurable lesions, ^a %	Non-target lesions	New, non-measurable lesions	Overall Response
Reduction of 100	Absent	Absent	irCR ^β
Reduction of 100	irNon-CR/Non-PD	Absent/Stable	irPR
Reduction of 100	Absent/Stable	irNon-CR/Non-PD	irPR
Reduction of ≥ 30	irNN	No unequivocal worsening	irPR
Reduction of < 30 to < 20 increase	Absence of unequivocal worsening		irSD
≥ 20 increase ^γ	Any	Any	irPD ^δ
Any	Unequivocal worsening	Any	irPD ^δ
Any	Any	Unequivocal worsening	irPD ^δ

Source: Bohnsack et al (2014)

TMTB = Total Measured Tumor Burden; irCR = immune-related Complete Response; irPR = immune-related Partial Response; irSD = immune-related Stable Disease; irPD = immune-related Progressive Disease. irNN = no target disease identified at baseline and at follow-up, the subject fails to meet the criteria for irCR or irPD.

^a Decreases assessed relative to baseline

^β Lymph nodes must also decrease to < 10 mm in short axis.

^δ At the time of unconfirmed progression, the baseline is reset and irPD is only achieved if an increase in tumor burden of 20% relative to the new baseline is observed.

^γ Minimum 5 mm absolute increase in TMTB compared to nadir

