2.2 Follow-up: Non-Target Lesion Assessment⁵	The RECIST v1.1 definitions for the assessment of non-target lesions apply. The response of non-target lesions primarily contributes to the overall response assessments of irCR and irNon-CR/Non-PD (irNN). Non-target lesions do not affect irPR and irSD assessments. Only a massive and unequivocal worsening of non-target lesions alone, even without progress in the TMTB is indicative of irPD.
2.3 Follow-up: New Non-Measurable Lesions Definition and Assessment⁶	All new lesions not selected as new measurable lesions are considered new non-measurable lesions and are followed qualitatively. Only a massive and unequivocal progression of new non-measurable lesions leads to an overall assessment of irPD for the timepoint. Persisting new non-measurable lesions prevent irCR.
2.4 irRC Overall Tumor Assessments^{7,8}	
irCR, complete disappearance of all measurable and non-measurable lesions. Lymph nodes must decrease to < 10 mm in short axis. Confirmation of response is not mandatory.
 
irPR, decrease of $\geq 30\%$ in TMTB relative to baseline, non-target lesions are irNN, and no unequivocal progression of new non-measurable lesions.
 
irSD, failure to meet criteria for irCR or irPR in the absence of irPD.
 
irNN, no target disease was identified at baseline and at follow-up the patient fails to meet criteria for irCR or irPD.
 
irPD⁹, minimum 20% increase and minimum 5 mm absolute increase in TMTB compared to nadir, or irPD for non-target or new non-measurable lesions. Confirmation of progression is recommended minimum 4 weeks after the first irPD assessment.
 
irNE, used in exceptional cases where insufficient data exists.
 
irND, in adjuvant setting when no disease is detected.

Source: [Bohnsack et al, 2014](#)

Key: TMTB = Total Measured Tumor Burden; irCR = immune-related Complete Response; irPR = immune-related Partial Response; irSD = immune-related Stable Disease; irNN = irNon-CR/Non-PD. irPD = immune-related Progressive Disease; irNE = immune-related not evaluable; irND = immune-related no measurable/non-measurable disease.

¹Up to 5 target lesions may be selected at baseline. Lesions will be measured unidimensionally. The minimum target lesion size at baseline in irRECIST is aligned with RECIST v1.1.

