In the case of SD, measurements must have met the SD criteria at least once after study entry at a minimum interval of 7 weeks. If the first post-baseline response assessment is an SD and the assessment was less than 7 weeks from first dose of study drug, then the SD would be changed to NE. For the dose escalation parts of the study (i.e., parts A, A2), the reporting of CR/PR does not require confirmation as the primary objective is safety. Confirmation is required for the expansion cohorts (i.e., Part B).

Table 1: Best Overall Response Algorithm

| Overall Response First Time Point | Overall Response Subsequent Time Point | Best Overall Response |
|-----------------------------------|--|---|
| CR | CR | CR |
| CR | PR | SD, PD, or PR ^a |
| CR | SD | SD provided minimum criteria for SD duration met, otherwise, PD |
| CR | PD | SD provided minimum criteria for SD duration met, otherwise, PD |
| CR | NE | SD provided minimum criteria for SD duration met, otherwise, NE |
| PR | CR | PR |
| PR | PR | PR |
| PR | SD | SD |
| PR | PD | SD provided minimum criteria for SD duration met, otherwise, PD |
| PR | NE | SD provided minimum criteria for SD duration met, otherwise, NE |
| NE | NE | NE |

CR = complete response, PR = partial response, SD = stable disease, PD = progressive disease, and NE = not evaluable.

^a If a CR is truly met at first time point, then any disease seen at a subsequent time point, even disease meeting PR criteria relative to baseline makes the disease PD at that point (since disease must have reappeared after CR). Best response would depend on whether minimum duration for SD was met. However, sometimes 'CR' may be claimed when subsequent scans suggest small lesions were likely still present and in fact the subject had PR, not CR at the first time point. Under these circumstances, the original CR should be changed to PR and the best response is PR.

Tumor burden assessed using RECIST v1.1 will be calculated as the sum of (the longest diameter of target non-nodal lesions plus the short axis of target nodal lesions). The percent change from baseline will be plotted by time on study as a spider plot. The maximum percent change from baseline will be plotted in a waterfall plot. The spider and waterfall plots will include all visits regardless of whether or not a response assessment has been recorded (as long as all baseline target lesions were measured at the visit).

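### Core Table 3 calls RECIST v1.1 progression at a 20% rise with no 5 mm minimum, unlike the Core's own irRECIST threshold; separately, the Core and the SAP measure target nodes differently

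*Protocol*

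**What the plan says.** **RECIST v1.1 rule in the Core.** Core 10.2.3.1 has the investigator assess target and non-target lesions by RECIST v1.1, citing the published guideline, "according to the categories and criteria described in the table below". That table is Table 3 in Core 10.2.4. Its target-lesion PD criterion is "At least a 20% increase in the sum of the LD of target lesions", referenced to the smallest sum since treatment started, or new lesions. It states no minimum in millimetres.

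**irRECIST rule in the Core.** The Table 5 footnote in Core 10.2.4.1 adds "Minimum 5 mm absolute increase in TMTB compared to nadir". Core 16.2 gives irPD as "minimum 20% increase and minimum 5 mm absolute increase in TMTB compared to nadir". Footnote 8 to Core 16.2 says the irPR and irPD thresholds follow RECIST v1.1.

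**Nodes.** Core 10.2.3.1 qualifies a node as measurable at "≥ 15 mm in short axis for nodal lesions", but then says "The sum of the longest diameter for all target lesions is to be calculated and recorded in the eCRF", with no exception for nodes. SAP 13.1.1 computes RECIST v1.1 tumour burden as the sum of "the longest diameter of target non-nodal lesions plus the short axis of target nodal lesions".

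**Use of the calls.** Under SAP 4.3 progression is by investigator assessment. SAP 13.1.2 dates response and progression from the scan linked to the reported assessment. The SAP gives no numerical PD threshold.

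**The concern.** The Core holds two versions of a threshold that it describes as the same, and the operative table for RECIST v1.1 carries the looser one. An investigator who follows Table 3 literally will call PD on growth of 2 to under 5 mm in a subject whose summed target lesions are small, either from the start or because the tumour has shrunk. PFS and DOR take their event dates from that call.

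Nothing later in the plan corrects it. No central reading is described, and the SAP works from reported assessments. The rule in Module section 9.2 that the SAP overrides the Core covers analyses, not how a scan was classified at the site.

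The node measure is a second, independent inconsistency. The SAP's spider and waterfall plots may rest on a different sum from the one behind the same subject's reported response.

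**Working it through.** The plan states no figure for this point, so there is none to reproduce. The check is arithmetic on the two PD rules.

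**Inputs**
- Table 3 (Core 10.2.4): PD when the increase is at least 0.20 × nadir sum.
- Core Table 5 footnote and Core 16.2: PD when the increase is at least max(0.20 × nadir sum, 5 mm).
- Smallest measurable non-nodal lesion, Core 10.2.3.1: "10 mm by CT or MRI scan for non-nodal lesions".
- PR, Core Table 3: at least a 30% decrease from baseline, so a sum of at most 0.70 × baseline.

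**Step 1: where the rules part.** They differ when 0.20 × nadir < 5 mm, that is, when nadir < 5 / 0.20 = 25 mm.

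| Nadir sum (mm) | Growth for PD, Table 3 (mm) | Growth for PD, 20% and 5 mm (mm) | Second rule as % of nadir |
|---|---|---|---|
| 10 | 2.0 | 5 | 50.0 |
| 12 | 2.4 | 5 | 41.7 |
| 15 | 3.0 | 5 | 33.3 |
| 20 | 4.0 | 5 | 25.0 |
| 24 | 4.8 | 5 | 20.8 |
| 25 | 5.0 | 5 | 20.0 |
| 30 | 6.0 | 6 | 20.0 |

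From 25 mm upward the rules are identical.

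**Step 2: when confirmation of a PR is at stake.** The choice of PD rule matters to confirmation at the next scan only if that scan is PD by Table 3 yet still within PR range of baseline: sum ≥ 1.20 × nadir and sum ≤ 0.70 × baseline. Both can hold only if nadir ≤ (0.70 / 1.20) × baseline = 58.3% of baseline, with nadir also below 25 mm.

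- Assumed case that qualifies: baseline 20 mm, nadir 11 mm (55% of baseline, −45%), next scan 13.5 mm. Change from nadir is 2.5 / 11 = +22.7%, or +2.5 mm. Change from baseline is 13.5 / 20 − 1 = −32.5%. Table 3 gives PD. With the 5 mm minimum, PD would need 11 + 5 = 16 mm, so the scan still meets PR. SAP Table 1 turns PR followed by PD into SD or PD, and the subject would drop out of DOR.
- Assumed case that does not: baseline 20 mm, nadir 14 mm (70%). Table 3 calls PD at 14 × 1.20 = 16.8 mm, but 16.8 / 20 − 1 = −16%, which is no longer PR under either rule. Confirmation fails at that scan either way; only the PD date changes.

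**Step 3: node measure (assumed values).**
- One node, longest diameter 20 to 25 mm, short axis 16 to 16 mm: +25% and +5 mm by longest diameter, 0% by short axis. PD only by longest diameter.
- Two nodes, each with longest diameter 25 to 25 mm and short axis 16 to 20 mm: 50 to 50 mm (0%) by longest diameter; 32 to 40 mm (+25%, +8 mm) by short axis. PD only by short axis.

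The direction is not fixed.

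**The case against.** The strongest reply is that published RECIST v1.1 governs. Core 10.2.3.1 cites it, Table 3 is sourced to it, and the Module and SAP name it throughout, so Table 3 can be read as an abbreviated summary. Some sites may indeed apply the publication directly. But the same sentence of the Core points investigators to the table's criteria, so the outcome is at best PD calls that vary between sites.

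A second reply is that the 5 mm text belongs to irRECIST, and footnote 8 is the only bridge to RECIST v1.1. That is true, but the bridge is explicit for the PD threshold. It does not extend to complete response. The requirement that nodes fall below 10 mm in short axis is stated only for irCR, and footnote 8 covers irPR and irPD, so the documents alone do not show that Table 3's CR wording is wrong.

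Third, the consequences are limited. PFS and DOR are secondary and descriptive. Module 4.4 allows treatment beyond progression in some circumstances, although that does not move the recorded PD date. These points stand as limits on importance.

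Several stronger readings are tempting but unsupported:
- That the SAP contains a 5 mm rule that Table 3 breaks. It does not; its only conflict with the Core here is over nodes.
- That summing longest diameters for nodes makes PD earlier. Step 3 shows it can go either way.
- That RECIST and irRECIST progression will diverge in this trial's analyses. SAP 4.2 accounts for all 99 treated subjects in monotherapy parts (37 + 39 + 10 + 3 + 10), and the SAP's response analyses use RECIST v1.1 only.
- That the calls fall within measurement error. The documents give no figure for it.

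**Conclusion.** The inconsistency is real and visible in the documents. For nadir sums below 25 mm, Core Table 3 calls target-lesion PD on less growth than the Core's own statement of the aligned threshold requires. The gap is largest for the smallest sums (2 mm against 5 mm at a 10 mm nadir) and closes at 25 mm. Where it bites, it can only bring PD forward, and so can shorten PFS and DOR. Loss of a confirmed PR at the next scan needs the further condition of a nadir at or below about 58% of baseline.

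This assumes that investigators applied Table 3 as written and that footnote 8 means what it says. The documents do not give the share of subjects with a nadir sum below 25 mm, so no effect on PFS, DOR or ORR can be stated. A reader might infer that the Part B response rate is materially at risk. The documents do not support that: only 3 subjects were treated in Part B, and the PR threshold itself is not in dispute.

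The node mismatch between Core 10.2.3.1 with Table 3 and SAP 13.1.1 also holds, as a separate inconsistency of unknown direction and size.

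**What to change.** 1. Amend Core 10.2.3.1 and Table 3 so that target-lesion PD needs at least a 20% and at least a 5 mm increase in the sum over nadir, matching Core 16.2, and so that nodal target lesions enter the sum by short axis, matching SAP 13.1.1. Reconcile the nodal CR wording with the cited RECIST v1.1 guideline. This is worth doing although enrolment has stopped, because the Module introduction says the same Core serves all first-in-human studies in the programme.
2. State the same PD rule in SAP 13.1.1.
3. Because rewording cannot change calls already recorded, re-derive target-lesion response, PFS and DOR from the recorded lesion measurements under that rule, as a sensitivity analysis beside the investigator-reported results. Report how many subjects had a nadir sum below 25 mm and how many calls changed.

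Two limits should be stated with the sensitivity analysis. Short axis can be used only where it was captured for nodes. Scheduled imaging runs until progression, so a subject whose PD call is removed may have no later scan and would be censored there.

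The cost is Core and SAP wording plus programming on existing data, with no extra visits or scans.
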